**15.11 STRATIFICATION HANDLING CONVENTION**

Stratification is not being implemented in this study.

RESTRUCTURED

**16.0**

**CHANGES TO ANALYSES SPECIFIED IN PROTOCOL**

There are no changes to the analyses specified in the final protocol Amendment 2 (version dated 06 Nov 2018). While there are analyses for endpoints collected during the OLTP that are with respect to Day 0 of the lead-in studies, it was necessary not to explicitly mention this fact in the RAP-MD-04 protocol Amendment 2 in order to protect restricted information pertaining to RAP-MD-01/02/03.

RESTRICTED

## **18.0**

## **APPENDICES**

### **APPENDIX I. TECHNICAL DETAILS FOR THE IMPLEMENTATION OF THE EXTENDED PLACEBO-BASED PATTERN MIXTURE MODEL VIA MULTIPLE IMPUTATION**

The following steps will be taken to implement the extended placebo-based pattern mixture model via multiple imputation:

1. Carry out a Bayesian analysis for the Cox proportional hazards model with treatment group as an explanatory variable and with piecewise constant baseline hazard function. Let  $h_0(t; \lambda) = \sum_{j=1}^J \lambda_j I(a_{j-1} \leq t < a_j)$  denote the piecewise constant baseline hazard function, where  $a_0 = 0 < a_1 < \dots < a_{J-1} < a_J = \infty$  denotes a partition of the time axis. The cut points are chosen to have an approximately equal number of events in each interval. The number of intervals with constant baseline hazard rates,  $J$ , is set to strike a balance between the approximation to the unknown underlying baseline hazard function and the number of events in each interval. The hazard function for patient  $i$  is  $h(t | X_i; \theta) = h_0(t; \lambda) \exp(\beta_1 X_{i1})$ , where  $X_{i1} = 1$  if patient  $i$  is in the rapastinel group.
2. Take a posterior draw of the model parameters,  $\tilde{\theta} = (\tilde{\lambda}, \tilde{\beta})$ , from the Bayesian analysis.
3. For a patient who prematurely discontinued without meeting any of the relapse criteria during the DBTP, impute the time to relapse after discontinuation,  $T_i$ , under the extended placebo-based pattern mixture model with sensitivity parameter  $\phi$ , by equating the conditional survival probability at  $T_i$  given that the patient discontinued at  $C_i$  to a uniform random variable  $U_i$ , that is,

[figure not shown]
$$\exp\left\{-\int_{C_i}^{T_i} h_0(t; \tilde{\lambda}) e^{(1-\phi)(\tilde{\beta}_1 X_{i1})} dt\right\} = U_i.$$

[figure not shown]
This equation can be easily solved by noting that the baseline hazard function  $h_0(t; \lambda)$  is piecewise constant.

4. If the imputed event time exceeds the planned follow-up time for the patient, we manage the patient as having no event by the end of the planned follow-up time. Thus, the imputed complete data set has no patients with premature discontinuation and has only administrative censoring at the planned follow-up time.

5. Apply the primary analysis model to the complete data set to obtain the parameter estimates and associated covariance matrix for a single imputation. The parameters are the log-rank test statistics for the log-rank test, and the log hazard ratios for the Cox model with treatment group as an explanatory variable.
6. Repeat Step 2 through Step 5 for  $m$  times to generate  $m$  sets of imputed complete-data parameter estimates and associated covariance matrices. Use the SAS procedure MIANALYZE to combine results from  $m$  imputed data sets and draw inference about the treatment effects of both rapastinel groups versus placebo.
7. Vary the value of the sensitivity parameter  $\phi \in \{0, 0.2, 0.4, 0.6, 0.8, 1\}$  in Step 3 to assess the robustness of the primary analysis results to the possible violation of the noninformative censoring assumption toward the informative censoring underlying the placebo-based pattern mixture model.

RESTRICTED

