## **2.0 INTRODUCTION**

This Statistical Analysis Plan (SAP) describes the methodology that will be used to summarize the statistical analyses of the efficacy and safety data for the final protocol Amendment 2 of Study RAP-MD-04 (version dated 13 Nov 2018).

Study RAP-MD-04 is a multicenter, double-blind, randomized, placebo-controlled, parallel-group study to evaluate the efficacy, safety, and tolerability of rapastinel as long-term maintenance treatment for patients with major depressive disorder (MDD) who completed 1 of the rapastinel lead-in studies (RAP-MD-01, RAP-MD-02, or RAP-MD-03). While the protocol was written to accommodate the potential recruitment of *de novo* patients, there were no *de novo* patients enrolled. Consequently, all analysis in this document pertains specifically to roll-over patients only.

The study will be conducted for the roll-over patients in the following periods:

- An 8- to 16-week, open-label treatment period (OLTP) where patients receive rapastinel 450 mg IV weekly
- A randomized, double-blind treatment period (DBTP) of at least 26 weeks (and up to 104 weeks) where patients are randomized 1:1:1 to either rapastinel 450 mg weekly, rapastinel 450 mg biweekly or placebo
- A 2-week safety follow-up period (for patients who do not enter the RAP-MD-06 extension study only)

In order for patients to transition from the OLTP and be randomized into the DBTP, the patient must meet the stable responder criterion sometime after 8 weeks (and up to 16 weeks) during the OLTP. A patient will be considered a stable responder upon achieving both criteria (1) and (2) below:

- 1) An observed Montgomery-Asberg Depression Rating Scale (MADRS) total score  $\leq 12$  with no more than one modest MADRS excursion (MADRS total score  $> 12$  but  $\leq 16$ ) for at least 6 consecutive weeks.
- 2) An observed MADRS total score  $\leq 12$  for at least 2 consecutive visits prior to randomization.

To meet these criteria a patient must have no missing MADRS assessments within the last 6 consecutive weeks prior to randomization.

The OLTP starts with the first dose of open-label treatment and ends with 1 of the following: the last scheduled assessment at the Visit 122/Early Termination for patients who do not enter the DBTP; the first dose of double-blind treatment for patients who enter the DBTP.

[figure not shown]

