The hypothesis testing will compare the time to first relapse between each rapastinel group and the placebo group using the log-rank test for the Double-blind mITT Population. Estimates of the hazard ratio and 95% CIs will be based on the Cox proportional hazards model with treatment group as an explanatory variable. The Kaplan-Meier estimates for the cumulative distribution of the relapse rate for each treatment group will be provided. The proportion of patients who relapse, the Kaplan-Meier estimate of the median, first quartile and third quartile of the time to first relapse and corresponding 95% CI for the median will be presented for each treatment group. Plots of the Kaplan-Meier estimate of the distribution of the time to first relapse will also be provided for each treatment group. The primary reason for relapse, as collected on the *Relapse CRF*, will be tabulated by treatment group.

Three sensitivity analyses will be performed to assess the robustness of the primary analysis results to the possible violation of the noninformative censoring assumption. The first sensitivity analysis assumes that patients who discontinued without meeting any of the relapse criteria during the first 52 weeks of the DBTP relapsed instead of being censored. The second sensitivity analysis will be based on the delta-adjusted method examined by Zhao et al (2014). The third sensitivity analysis is an extension of the placebo-based pattern mixture model proposed by Lu (2014, 2015). The placebo-based pattern mixture model assumes that patients who discontinued from the rapastinel treatment groups would have disease progression after discontinuation similar to that of placebo. The extended placebo-based pattern mixture model uses a sensitivity parameter to characterize the gradual deviation from the noninformative censoring underlying the primary analysis toward the informative censoring underlying the placebo-based pattern mixture model. The extended placebo-based pattern mixture model sensitivity analysis for time-to-event data is described as follows:

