Let  $h_0(t)$  denote the baseline hazard function associated with the placebo group. Let  $\beta_1$  and  $\beta_2$  denote the treatment effects in terms of log hazard ratios under noninformative censoring for rapastinel 450 mg weekly versus placebo and rapastinel 450 mg biweekly versus placebo, respectively. The hazard functions associated with the rapastinel 450 mg weekly and 450 mg biweekly groups under noninformative censoring are thus given by  $h_1(t) = h_0(t) \exp(\beta_1)$  and  $h_2(t) = h_0(t) \exp(\beta_2)$ , respectively. Consider the extended placebo-based pattern mixture model sensitivity analysis. For the placebo group, we assume that patients with premature discontinuation would have comparable experience after discontinuation to their counterparts without premature discontinuation. For the rapastinel treatment groups, each dropout timepoint for rapastinel patients defines a missing data pattern, and we assume that patients with premature discontinuation would have disease progression after discontinuation somewhere between their counterparts without premature discontinuation and patients in the placebo group. Specifically, we assume that  $h_1(t) = h_0(t) \exp((1-\phi)\beta_1)$  and  $h_2(t) = h_0(t) \exp((1-\phi)\beta_2)$  for  $t > C$ , where  $C$  denotes the time of premature discontinuation. The sensitivity parameter  $\phi \in [0,1]$  characterizes the gradual deviation from the noninformative censoring with  $\phi = 0$  toward the informative censoring underlying the placebo-based pattern mixture model with  $\phi = 1$ . A multiple imputation approach will be used to implement the extended placebo-based pattern mixture model.

Technical details for the implementation of the sensitivity analyses are provided in [APPENDIX I](#).

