**13.0**

**DETERMINATION OF SAMPLE SIZE**

The sample size and power calculations are based on the analysis of time to relapse during the first 52 weeks of the DBTP. Assuming a relapse rate of 19% per 26 weeks in the placebo group and a dropout rate of 20% per 26 weeks in all treatment groups, the sample size of 200 per group will have 90% power to detect a hazard ratio of 0.475 for a rapastinel treatment versus placebo at a 0.05 significance level. To achieve this number of randomized patients, approximately 1500 patients need to be enrolled in this study if 40% of patients are qualified for randomization.

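### Appendix I imputes relapse with one pooled rapastinel effect although Section 8.1 defines two, so φ = 0 does not return the primary hazard ratios when the arms differ

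*SAP*

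**What the plan says.** SAP Section 2.0 describes three arms: "patients are randomized 1:1:1 to either rapastinel 450 mg weekly, rapastinel 450 mg biweekly or placebo". Section 8.1 sets up the extended placebo-based pattern mixture model with β₁ and β₂ as log hazard ratios "for rapastinel 450 mg weekly versus placebo and rapastinel 450 mg biweekly versus placebo, respectively". After discontinuation the weekly arm has hazard h₀(t)exp((1−φ)β₁) and the biweekly arm h₀(t)exp((1−φ)β₂). The parameter φ is there "to characterize the gradual deviation from the noninformative censoring underlying the primary analysis", so φ = 0 is the primary analysis's own assumption. Section 8.1 refers to Appendix I for implementation.

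Appendix I, Step 1, gives the hazard as h₀(t; λ)exp(β₁Xᵢ₁), where Xᵢ₁ = 1 if the patient "is in the rapastinel group". Step 3 imputes with exp((1−φ)β₁Xᵢ₁). Neither step has a second coefficient or indicator. Step 6 nevertheless combines the imputed data sets to "draw inference about the treatment effects of both rapastinel groups versus placebo".

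**The concern.** The model in Section 8.1 and the formula meant to implement it disagree. No single arm is the rapastinel group, so the natural literal reading sets Xᵢ₁ = 1 in both active arms and fits one common effect. Dropouts from the stronger arm are then imputed with too high a relapse hazard, and those from the weaker arm with too low a one. Steps 5 and 6 still estimate each arm against placebo, so the two estimates are pulled towards each other.

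The φ series is read as movement away from its φ = 0 anchor. If the anchor has already moved for a reason unrelated to censoring, the stronger arm looks less robust to informative dropout than it is, and the weaker arm more robust.

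**Working it through.** **Inputs from SAP Section 13.0.** Placebo relapse 19% per 26 weeks, dropout 20% per 26 weeks in all arms, 200 per arm, analysis over 52 weeks, and 90% power "to detect a hazard ratio of 0.475 for a rapastinel treatment versus placebo".

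**Assumptions.** Exponential times, everyone followed to week 52 unless they relapse or drop out, weekly hazard ratio 0.475. The SAP gives no separate biweekly hazard ratio, so a range of 0.475 to 1.0 is used.

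**Hazards per week.** Placebo λ₀ = −ln(0.81)/26 = 0.00810; dropout μ = −ln(0.80)/26 = 0.00858.

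**Reproducing the plan's power.** Expected events per arm are D = 200·λ/(λ+μ)·(1 − e^(−52(λ+μ))). This gives 56.3 on placebo and 29.5 on weekly, 85.8 in total. Freedman: Φ(√85.8 × 0.525/1.475 − 1.96) = 90.9%. Schoenfeld gives 93.2%. The stated 90% is reproduced, so the inputs are sound.

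**Analytic check at φ = 0, biweekly 0.80.**

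1. Person-weeks are P = D/λ: weekly 29.5 events in 7,659; biweekly 46.8 in 7,210.
2. The pooled rapastinel hazard is r = (29.49 + 46.75)/(7,659 + 7,210) = 0.00513, a hazard ratio of 0.00513/0.00810 = 0.63. Dropouts from both arms are imputed with it, instead of 0.475 and 0.80.
3. Expected imputed events by week 52 are 200·∫₀⁵² μe^(−(λ+μ)c)(1 − e^(−r(52−c)))dc: 8.85 weekly and 8.49 biweekly. The added person-weeks are these divided by r: 1,727 and 1,657.
4. Completed-data rates: weekly (29.49 + 8.85)/(7,659 + 1,727) = 0.00408; biweekly (46.75 + 8.49)/(7,210 + 1,657) = 0.00623.
5. Divided by λ₀ (0.0081047): **0.504** and **0.769**, against true values of 0.475 and 0.80.

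**Simulation of Steps 1 to 6.** 1,000 three-arm trials per scenario, four equal-event baseline intervals (assumed), normal-approximation posterior draws, 20 imputations, Cox model on all three arms, Rubin's rules. Hazard ratios are geometric means; the Monte Carlo SE of the log-HR shift at φ = 0 is at most 0.002. Percentages were taken before rounding.

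| Assumed biweekly HR | Weekly: primary → pooled, φ = 0 | Biweekly: primary → pooled, φ = 0 |
|---|---|---|
| 0.475 | 0.475 → 0.474 (no material shift) | 0.472 → 0.473 (no material shift) |
| 0.60 | 0.476 → 0.489 (+2.6%) | 0.601 → 0.590 (−1.9%) |
| 0.70 | 0.476 → 0.497 (+4.5%) | 0.704 → 0.683 (−3.0%) |
| 0.80 | 0.471 → 0.501 (+6.3%) | 0.798 → 0.767 (−3.9%) |
| 1.0 | 0.475 → 0.522 (+9.9%) | 1.005 → 0.955 (−5.0%) |

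The two-term model returns the primary hazard ratios within 0.1% in every row. A simpler simulation (one constant-hazard interval, 300 trials, 10 imputations, true 0.475/0.80) agrees: primary 0.475/0.791, two-term 0.475/0.791, pooled 0.504/0.763.

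**Along the φ series.**

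- Biweekly 0.80: the +6.3% weekly artefact at φ = 0 is as large as the whole effect of φ = 0.4 under the two-term model (+6.3%).
- Biweekly 0.70, φ = 0.4: the pooled model moves biweekly only from 0.704 to 0.708, the two-term model to 0.723.
- φ = 1: the treatment term vanishes and the two models agree (0.566/0.836 in both, biweekly 0.80).

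**Against sampling error.** The SE of the weekly log hazard ratio is about √(1/56.3 + 1/29.5) = 0.23. With biweekly 0.80, the weekly shift is ln(1.063) = 0.061, about a quarter of an SE. The biweekly shift is ln(0.961) = −0.040 against √(1/56.3 + 1/46.8) = 0.20, about a fifth.

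**The case against.** The strongest reply is that the SAP already shows what is meant. Section 8.1 has both coefficients, Step 1 names treatment group as the explanatory variable as the primary Cox model does, and Step 6 covers both arms. A programmer reading all three would probably fit two terms. That is fair: this looks like a dropped term, not a decision to pool. But Appendix I is the implementing text, and the same omission stands in two formulas and in the definition of the indicator.

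A second reply is that the steps could be run separately for each arm against placebo. One coefficient would then suffice and φ = 0 would recover the primary result. The appendix does not say so, and it sits badly with one model in Step 1 and with inference on both arms from the same m data sets in Step 6.

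The points on size stand. Every non-zero shift in the table needs an assumed biweekly effect different from weekly. The shifts are a fraction of a standard error, and the largest need a biweekly arm with little or no effect. For weekly, the first comparison in the testing sequence, the error is conservative. It fades towards φ = 1, the most demanding setting. No changed sensitivity conclusion has been shown.

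A further reading, Xᵢ₁ = 1 for weekly only, would do more harm: with both true hazard ratios 0.475, biweekly moves from 0.472 to 0.547 (+16%). It fits the printed words less well, so the conclusion does not rest on it.

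**Conclusion.** The point holds. Appendix I, Steps 1 and 3, contradict Section 8.1, and followed as printed they break the φ = 0 anchor whenever the two arms differ. At planning rates with weekly at 0.475, the shift at φ = 0 is +2.6% to +9.9% for weekly and −1.9% to −5.0% for biweekly as the assumed biweekly hazard ratio runs from 0.60 to 1.0; it is nil if the arms are equal. These figures rest on exponential times, follow-up to week 52 and a pooled reading of the single indicator.

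The reach is limited to one of three sensitivity analyses, outside the testing sequence of Section 8.2. Primary estimates, Type I error and power do not change. It should be corrected because the formula is wrong as written and the shift can be mistaken for an effect of informative censoring.

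**What to change.** In Appendix I, Step 1, write h(t | Xᵢ; θ) = h₀(t; λ)exp(β₁Xᵢ₁ + β₂Xᵢ₂), with Xᵢ₁ = 1 for weekly, Xᵢ₂ = 1 for biweekly, and both 0 for placebo. In Step 3, replace the exponent by (1−φ)(β₁Xᵢ₁ + β₂Xᵢ₂). Add a check that the φ = 0 run reproduces the primary hazard ratios within Monte Carlo error; it would expose either misreading if it were programmed. If separate runs per arm against placebo were intended, the appendix should say so.

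The cost is one added term in two formulas and a line defining the indicators. No data collection or patient procedure is affected.

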**RESTRICTED**

**19.0**

**HISTORY OF CHANGES**

Date	Section	Description
11/29/2018	NA	Initial version approval.

**RESTRUCTURED**
